Nothing herein is to be disclosed in any way without the prior
express written permission of W. L. Gore & Associates, Inc.

**GORE® Septal Occluder Clinical Study: A Study to evaluate safety and efficacy in the
treatment of transcatheter closure of *ostium secundum* atrial septal defects (ASDs)**

Protocol Number: GSO 10-09

Original Protocol: 26 June 2012

Amendment Date: 22 August 2014

W. L. Gore & Associates, Inc.
Medical Products Division
[name]

[contact]
[contact]

CONFIDENTIAL INFORMATION

Study Information

Study Title	GORE® Septal Occluder Clinical Study: A Study to evaluate safety and efficacy in the treatment of transcatheter closure of ostium secundum atrial septal defects (ASDs)
Protocol Number	GSO 10-09
Sponsor	W. L. Gore & Associates, Inc. Medical Products Division [name] [contact] [contact]
Study Design	Prospective, mulitcenter, single-arm, clinical study comparing the GORE® Septal Occluder to outcomes from previous GORE® HELEX Septal Occluder clinical studies.
Study Objective	To evaluate the safety and efficacy of the GORE® Septal Occluder in the treatment of percutaneous, transcatheter closure of ostium secundum atrial septal defects (ASDs).
Study Endpoints	
Primary Endpoint Composite Clinical Success evaluated at 6 months post-procedure
 
Secondary Endpoints
 
 • Technical Success • Procedure Success • Closure Success • Safety
Patient Population	
Patients with:
 
 • ostium secundum atrial septal defects of ≤ 17 mm measured by stop flow balloon sizing • evidence of right ventricular volume overload • absence of concurrent cardiac defect(s) that could elevate morbidity/mortality beyond what is common for ASD (e.g. Large ventricular septal defect, hypoplastic left heart syndrome, coarctation, arrhythmias requiring electrophysiology or concurrent intervention with device placement)
Number of Sites	Up to 21 sites
Enrollment	400 total subjects in following phases: 50 Pivotal 350 Continued Access Post Approval (if required)
Study Duration	
Enrollment Duration:
 
Pivotal Phase: 7 months
 
Continued Access Phase: 12-20 months
 
Post Approval Phase: (if required post PMA approval)

CONFIDENTIAL INFORMATION

	
Pivotal Study Duration: 13-16 months Overall Study Duration: 5-6 years based on 36 months follow up for enrolled subjects

Pre-Enrollment Evaluation	
Pre-procedural exam performed within 6 months of procedure that must include:
 
  confirmation of ASD by TTE or TEE  estimated defect size $\leq 17\text{mm}$  ECG 
Subjects will be considered enrolled when the GORE® Septal Occluder device is introduced into the anatomy of the subject.

Follow-Up Evaluations	
Subjects successfully enrolled in the study will be examined at 30 days and 6 months after the procedure. Each visit will include:
 
  physical exam  ECG  TTE  Fluoroscopy-En face and lateral views (6 months)* 
Long term follow-up will be performed at 12, 24 and 36 months. The 12 and 36 month visits will include:
 
  physical exam  ECG  TTE  Fluoroscopy-En face and lateral views (36 months)* 
The 24 month visit by telephone follow-up questionnaire.
 
* Refer to Section 5.4.8 for details.

Echocardiographic Core Laboratories	
[name], FACC, FASE Director, Non-Invasive Cardiac Imaging Arnold Palmer Hospital for Children Orlando FL
 
[name] Assistant [name] Children's Hospital Baylor College of Medicine Pediatric Cardiology Houston TX

Study Clinical Monitor	
Theorem Clinical Research [contact] www.theoremclinical.com

IDE or PMA Number	G110161

CONFIDENTIAL INFORMATION

LIST OF ABBREVIATIONS

AE	Adverse Event
ASD	Atrial Septal Defect
CD	Compact Disc
CDMS	Clinical Data Management System
CFR	Code of Federal Regulations
Cm	Centimeter
CRF	Case Report Form
CRO	Contract Research Organization
ECG	Electrocardiogram
eCRF	Electronic Case Report Form
ePTFE	expanded polytetrafluoroethylene
FDA	Food and Drug Administration
Fr	French Catheter Scale
GCP	Good Clinical Practice
ICF	Informed Consent Form
ICH	International Conference on Harmonisation
ICE	Intracardiac Echocardiography
IDE	Investigational Device Exemption
IDR	Independent Data Reviewer
IRB	Institutional Review Board
MedDRA	Medical Dictionary for Regulatory Activities
mm	Millimeter
O.D.	Outer diameter
PAS	Post Approval Study
PMA	Pre-Market Approval

1.0 Introduction

W. L. Gore & Associates, Inc., has developed an atrial septal defect (ASD) closure device, the GORE® Septal Occluder. This minimally invasive occluder device is intended to effectively repair *ostium secundum* ASDs.

Ostium secundum atrial septal defects present as a persistent communication between the atria and are a common congenital cardiac anomaly accounting for approximately 10% of all congenital heart disease. They are one of the most common congenital heart defects to present in adulthood. Untreated, ASDs produce right heart volume overload and progressive impairment over time, including reduced aerobic capacity, atrial dysrhythmias, congestive heart failure, pulmonary hypertension, and potential paradoxical embolism. In the U.S. alone it is estimated that approximately 10,000 new patients per year can be expected to have an ASD. Successful surgical repair of ASD has been performed for 50 years with continued improvement in technique and outcomes. King and Mills reported the first transcatheter closure of ASD in 1976, but the delivery system was quite large and impractical, especially for younger patients. With time, improvements in design concepts and materials discoveries have led to improved results in transcatheter closure systems. Several devices are now available commercially for transcatheter ASD closure.

The primary objective of the GORE® Septal Occluder Study is to evaluate the safety and efficacy of the occluder device in the treatment of transcatheter closure of *ostium secundum* atrial septal defects (ASDs). The data obtained in this study will evaluate this next generation device as compared to outcomes of prior studies conducted with the GORE® HELEX® Septal Occluder.

1.1 Device Description

1.1.1 GORE® Septal Occluder

The GORE® Septal Occluder consists of an implantable occluder and a catheter delivery system. The occluder is comprised of five platinum-filled nickel-titanium (Nitinol) wires which form a frame covered with expanded polytetrafluoroethylene (ePTFE). The ePTFE is treated with a hydrophilic coating to facilitate echocardiographic imaging of the occluder and surrounding tissue during implantation. When fully deployed, the occluder assumes a configuration (see Figure 1) to prevent shunting of blood between the right and left atria.

CONFIDENTIAL INFORMATION

The occluder is configured in nominal diameters of 15, 20, 25, and 30mm. The occluder is delivered using conventional catheter delivery techniques and may be delivered with the aid of a 0.035" guidewire, or smaller, if necessary.

[figure not shown]

Figure 1: GORE® Septal Occluder

1.2 GORE® Septal Occluder Delivery System

The delivery system consists of a 75 cm working length 10 Fr (O.D.) delivery catheter, a control catheter, and a mandrel coupled to a handle (Figure 2). The handle facilitates loading, deployment, and locking of the occluder. The handle also allows repositioning and retrieval of the occluder via the retrieval cord, if necessary.

The catheter delivery system for the GORE® Septal Occluder is a catheter and handle assembly composed of four primary components.

- **Delivery Catheter:** Delivers the occluder to the treatment site.
- **Control Catheter:** Advances/retracts the occluder at the treatment site.
- **Mandrel:** Supports the Nitinol frame and the locking mechanism of the occluder.
- **Handle:** Facilitates simple push/pull motions for occluder loading, deployment, and locking.

The catheter components are arranged coaxially and are coupled to the handle mechanism. The handle moves the catheter components separately or in combination to facilitate simple push/pull motions for occluder loading, deployment, and locking. The retrieval cord attaches the proximal eyelet of the occluder to the control catheter and facilitates occluder retrieval after lock

CONFIDENTIAL INFORMATION

release, if necessary. A flexible flushing port is attached to the handle to permit convenient device flushing prior to implant.

[figure not shown]

Figure 2: GORE® Septal Occluder Handle Delivery System

2.0 Study Objectives

2.1 Primary Objective

The primary objective of this study is to evaluate the safety and effectiveness of the GORE® Septal Occluder when used for percutaneous, transcatheter closure of *ostium secundum* atrial septal defects (ASDs).

3.0 Study Design

3.1 Description of Study Design

This is a prospective, multicenter, single arm, clinical study comparing outcomes with the GORE® Septal Occluder to outcomes from previous GORE® HELEX® Septal Occluder clinical studies.

[figure not shown]
This study will enroll 150 - 400 subjects from a maximum of 21 sites. Enrollment will occur in three phases – Pivotal (50 subjects), Continued Access (100 - 350 subjects), and Post Approval (if required). Each phase will enroll sequentially (see Study Schema). Criteria for initiation of each phase of enrollment are presented in Section 10.5.

All enrolled subjects will be followed through the 36-month, post index procedure follow-up. The study primary endpoint, composite Clinical

CONFIDENTIAL INFORMATION

Success, will be evaluated at 6 months post index procedure. The analysis in support of pre-market approval submission will occur when the 50 Pivotal subjects have completed 6-month follow-up evaluations. The final, primary endpoint analysis of Clinical Success will occur when all enrolled subjects have completed 36-month follow-up evaluations.

3.2 Study Endpoints

3.2.1 Primary Endpoint

The primary endpoint for the study is composite Clinical Success evaluated at 6 months post index procedure and is defined as satisfying all the following criteria:

1. Successful deployment and retention (at conclusion of index procedure) of a GORE® Septal Occluder
2. Freedom from:
 - any Serious Adverse Event (SAE) through 30 days post procedure
 - device events (post-procedure embolization, device removal, or other device reintervention) from completion of the implant procedure through the 6-month follow-up evaluation
3. A clinical residual defect status of completely occluded or clinically insignificant residual shunt at 6-month evaluation as determined by the Echo Core Lab (see Section 3.2.3)

3.2.2 Secondary Endpoints

Technical Success: Successful deployment and retention of a GORE® Septal Occluder device at the conclusion of the index procedure.

CONFIDENTIAL INFORMATION

Procedure Success: Technical Success with the GORE® Septal Occluder and ≤ 2 mm residual shunt of the target ASD at conclusion of the index procedure.

Closure Success (Efficacy): Technical Success and measured residual defect status of occluded/trivial, evaluated at 6 months, 12 months, and 36 months post index procedure.

Safety: A calculation of the proportion of subjects experiencing one or more Serious Adverse Event(s) (SAE) in the first 30 days post index procedure and/or a device event (embolization, device removal, reintervention after completion of index procedure) through 6 months, 12 months, and 36 months post index procedure.

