5.4.3 Enrollment

A subject is considered enrolled into the clinical study when the GORE® Septal Occluder device is introduced into the anatomy of the subject. Subjects who enroll in the trial and have a successful implant should be followed through 36 months post index procedure (see Study Schema, Section 5.1).

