Subjects with unsuccessful placement of a GORE® Septal Occluder (no study device implanted at conclusion of index procedure) will be followed through 30 days post index procedure. Subjects will be contacted by phone at 30 days for follow-up; upon completion of the telephone follow-up Case Report Form (CRF) at the 30-day Unsuccessful Implant interval, subject is discontinued from the study. These subjects will be considered enrolled and a technical failure for purposes of study analysis.

CONFIDENTIAL INFORMATION

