5.5 Subject Withdrawal from the Clinical Study

A subject may withdraw from the clinical study at any time and for any reason, and should notify the Investigator in this event. Subjects are not obligated to reveal their reasons for withdrawal. The subject will be withdrawn if he/she relocates to another geographic area that requires a change of physician and such suitable physician cannot be identified.

The Investigator may withdraw the subject from the clinical study at any time based on his/her medical judgment. It is important that the Investigator encourage subjects to return for all required follow-up visits within the designated window. The clinical study objectives may not be realized if a significant number of subjects are lost to follow-up. A subject may withdraw, or be withdrawn by the Investigator, if he or she is unable to continue participation in the study due to any condition unrelated to the study.

The Investigator or designee must complete the appropriate CRF (Study Completion/Discontinuation Form) documenting the subject's withdrawal or discontinuation from the clinical study. The subject will be considered withdrawn once the Sponsor receives the respective CRF.

At any time other than the immediate index procedure during the study where complications prevent retention of the GORE® Septal Occluder (i.e., embolization or other event requiring device removal), the subject will be discontinued from further study follow-up. All adverse events will be collected and reported in compliance with this protocol through the point of device removal. The Investigator or designee will complete the Study Completion/Discontinuation Form documenting the subject's discontinuation from the clinical study.

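### Safety through 12 and 36 months is a crude proportion with no stated denominator and no rule for subjects lost before those times, so the late device-event rate can be biased in either direction

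*Combined protocol and SAP*

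**What the plan says.** Section 3.2.2 builds Safety from two parts joined by and/or. The early part is "A calculation of the proportion of subjects experiencing one or more Serious Adverse Event(s) (SAE) in the first 30 days post index procedure". The long-term part is "a device event (embolization, device removal, reintervention after completion of index procedure) through 6 months, 12 months, and 36 months post index procedure". SAEs after day 30 therefore do not enter; only device events do.

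Section 10.6.4 makes all secondary endpoints descriptive. Section 10.6.2 defines a per-protocol set (no eligibility violations, evaluated through 6 months) and an intent-to-treat set (everyone enrolled), and assigns neither to Safety. No censoring rule or time-to-event estimate is given.

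Follow-up differs by outcome:
- **Successful implants:** under section 5.4.3, subjects who enroll and "have a successful implant should be followed through 36 months post index procedure".
- **Failed implants:** under section 5.4.6, subjects left without a study device "will be followed through 30 days post index procedure" and then leave the study. "These subjects will be considered enrolled and a technical failure for purposes of study analysis".
- **Later loss of the device:** under section 5.5, "the subject will be discontinued from further study follow-up".
- **Lost to follow-up:** under section 5.6, a missed visit plus three documented contact attempts can end participation.

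Section 3.1 says instead that "All enrolled subjects will be followed through the 36-month, post index procedure follow-up", and section 10.5 also speaks of all subjects being followed to 36 months. Section 10.4 allows for up to 10% loss before 6 months and gives no later figure.

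**The concern.** A proportion through 36 months is well defined only if every subject in the denominator is observed to 36 months or to an event. Here some will not be. The plan does not say whether a subject last seen at month 8 stays in the denominator as event-free or is dropped from it. The two choices move the estimate in opposite directions, and the choice could be made after the data are seen.

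The 12- and 36-month Safety figures are the study's long-term summary of embolization, removal and reintervention. A time-to-event estimate uses each subject's observed time, so it needs neither choice.

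**Working it through.** **The plan's own figure.** The documents state no number for Safety. The only attrition figure is the 10% before 6 months in section 10.4, which reproduces: 135 / (1 − 0.10) = 150. Continued at the same pace, an extrapolation that the plan does not make, it gives 1 − 0.9² = 19% by 12 months and 1 − 0.9⁶ = 46.9% by 36 months.

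**Assumptions.** True device-event risk F = 5% by T = 36 months among implanted subjects; dropout D = 10%, 20% or 30% by 36 months, with 46.9% as an extreme; constant hazards; dropout unrelated to event risk.

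**Formulas.** λ = −ln(1 − F)/T and γ = −ln(1 − D)/T.
- Events seen, as a fraction of all implanted: O = λ/(λ + γ) × [1 − exp(−(λ + γ)T)]
- Event-free completers: C = (1 − F)(1 − D)
- All-implanted denominator reports O. Known-status denominator reports O/(O + C).

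Example at D = 20%: λT = 0.0513 and γT = 0.2231. O = 0.0513/0.2744 × (1 − 0.76) = 0.0449. C = 0.95 × 0.80 = 0.76. Known status = 0.0449/0.8049 = 0.0557.

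| Dropout by 36 months | All implanted | Relative | Known status | Relative |
|---|---|---|---|---|
| 10% | 4.7% | −5% | 5.3% | +5% |
| 20% | 4.5% | −10% | 5.6% | +11% |
| 30% | 4.2% | −16% | 6.0% | +19% |
| 46.9% | 3.7% | −26% | 6.9% | +37% |

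At 12 months, with 5% / 10% / 19% dropout, the all-implanted figure is about 2% / 5% / 10% too low in relative terms.

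**Early events.** Suppose 80% of device events come before any dropout. Then 4% is fully observed, and the remaining risk is (0.05 − 0.04)/(1 − 0.04) = 1.04%. The all-implanted figure is 4.95% / 4.90% / 4.84% at 10% / 20% / 30% dropout, a relative shortfall of 1% to 3% (5% at 46.9%).

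**Full composite, all enrolled.** Add assumed values of 5% failed implants and a 5% 30-day SAE risk in everyone. Truth: 0.95 × (1 − 0.95 × 0.95) + 0.05 × 0.05 = 9.51%. Reported: 0.95 × (0.05 + 0.95 × O) + 0.05 × 0.05 = 9.28% / 9.05% / 8.80% at 10% / 20% / 30% dropout, about 2% to 7% too low in relative terms.

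**Failed implants.** Their SAE component closes at day 30, when their follow-up ends, and they carry no study device that could later embolize, be removed or need reintervention. Without any dropout, including 2% / 5% / 10% of them changes the composite from 9.75% (implanted only) to 9.66% / 9.51% / 9.28%. These are correct values for a different denominator; no event is missed. One small gap remains: the 30-day call has a ±14-day window, so a call at day 16 could miss a late 30-day SAE.

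**A trap in the remedy.** Kaplan-Meier over all enrolled subjects, with failed implants censored at day 30, treats them as still at risk of device events. With 5% failures and a 5% per-implant risk, the true all-enrolled risk is 0.95 × 5% = 4.75%, but that estimate returns about 5%.

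**The case against.** The strongest reply is that the endpoint is descriptive. No test, sample size or success rule depends on it, and a descriptive presentation does not exclude a Kaplan-Meier curve. That stands, and it limits the point to a cheap improvement. It does not supply the missing denominator.

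Three stronger readings are tempting, and the documents do not support them.

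1. *That 30-day follow-up of failed implants hides long-term events.* It does not, because sections 3.2.2 and 5.4.6 together leave these subjects no later endpoint event to miss. A calculation that spreads events evenly over 36 months and gives failed implants such events, with 5% failures, yields reported-to-true ratios of 0.95 × (1 − 0.10/2) = 0.90 and 0.95 × (1 − 0.30/2) = 0.81, a shortfall of 10% to 19%. The factor 0.95 is an artefact. Without it the ratios are 0.95 and 0.85, before allowing for the early SAE part of the composite.
2. *That the rate is necessarily understated.* No denominator is stated, and a known-status denominator overstates it.
3. *That every device removal would vanish because removal ends participation.* This would follow only from a denominator of 36-month completers that also excludes subjects with events. Section 3.2.2 names removal as an endpoint event and section 5.5 collects adverse events up to removal, so that reading is implausible. The plan should still rule it out in words.

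**Conclusion.** The point holds in limited form. Safety at 12 and 36 months is a crude proportion with neither a denominator nor a rule for incomplete follow-up. An all-enrolled or all-implanted denominator understates late device events, and a known-status denominator overstates them. With an assumed 5% true 36-month rate and 30% dropout, the same data could be reported as 4.2% or 6.0%; at 10% dropout, as 4.7% or 5.3%. If events come early the all-implanted shortfall is a few percent in relative terms, and for the full composite over all enrolled it is about 2% to 7%.

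These sizes rest on assumed event and dropout rates, since the documents give neither beyond 6 months, and on dropout being independent of event risk. Kaplan-Meier needs the same independence. Separately, sections 3.1 and 10.5 conflict with section 5.4.6 on how long failed implants are followed.

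**What to change.** In sections 3.2.2 and 10.6.4:

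- Report 30-day SAEs as a proportion of all enrolled subjects.
- Report device events at 6, 12 and 36 months among subjects with a successful implant, as a Kaplan-Meier estimate or a cumulative incidence with death as competing event. Count removal as an event, censor at last contact, and give the 95% confidence interval and number at risk.
- If the composite is also reported for all enrolled subjects, do not censor failed implants at day 30 as though they were still at risk of device events.
- Keep the crude count beside the estimate and state its denominator.
- Reconcile sections 3.1 and 10.5 with section 5.4.6 on follow-up of failed implants.

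The cost is a little more analysis work and possibly a slightly less favourable long-term figure. Adverse event onset dates are already collected (section 9.6), and reinterventions and discontinuations have their own forms (sections 5.4.9 and 5.5). No new visits or subjects are needed.

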5.4.9 Reinterventions

Reinterventions to the study device (GORE® Septal Occluder) will be reported on the Intervention CRF. If the GORE® Septal Occluder is removed as part of the reintervention, then the subject is discontinued from the study. If the GORE® Septal Occluder remains implanted, then the subject will continue to be enrolled and will complete study follow-up as prescribed.

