10.5 Study Enrollment

Enrollment in the GORE® Septal Occluder study will occur in three phases:

1. Pivotal cohort of 50 subjects from a maximum of 10 sites.
Enrollment in this phase will begin upon Investigational Device Exemption (IDE) approval. Upon completion of 6 month follow up for all 50 subjects, a submission will be made to FDA for Pre-Market Approval (PMA).
2. Continued Access cohort of 100 – 350 subjects from 10 – 21 (up to 11 additional) sites. Enrollment in this phase will begin after FDA acceptance of 30-day safety analysis on the Pivotal cohort.
3. Post Approval cohort of subjects will be enrolled depending on the number achieved in Continued Access upon PMA approval.
Enrollment in this phase will begin after FDA pre-market approval for GORE® Septal Occluder. (Post Approval Study [PAS] subjects will be enrolled pursuant to the approval of this protocol and PMA.)

Total enrollment for the GORE® Septal Occluder study will be 150 – 400 subjects. All subjects will be enrolled and followed under the same criteria through the 36 months post index procedure.

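### Adverse event collection stops at device removal, so harms after an explant, even within the 30-day SAE window, fall outside routine collection; the follow-up statements need reconciling

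*Combined protocol and SAP*

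**What the plan says.** **After device removal.** Section 5.5 covers any loss of the device after the index procedure, by embolization or another event that requires removal. The subject leaves follow-up, and "All adverse events will be collected and reported in compliance with this protocol through the point of device removal". Section 5.4.9 repeats this for reinterventions: if the occluder "is removed as part of the reintervention, then the subject is discontinued from the study". If the device stays in, the subject stays in.

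**General follow-up statements.** Section 3.1: "All enrolled subjects will be followed through the 36-month, post index procedure follow-up". Section 10.5: "All subjects will be enrolled and followed under the same criteria through the 36 months post index procedure". Section 5.4.3 limits itself to subjects who enroll and "have a successful implant should be followed through 36 months post index procedure". None of the three mentions removal.

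**Never-implanted subjects.** Under Section 5.4.6 they "will be followed through 30 days post index procedure", by a telephone contact at which the Section 5.2 schedule requires adverse events to be assessed.

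**Endpoints.** Safety (Section 3.2.2) is the proportion of subjects with one or more events of the type "SAE) in the first 30 days post index procedure and/or a device event (embolization, device removal, reintervention" after the index procedure), read at 6, 12 and 36 months. The primary composite (Section 3.2.1) uses the same SAE window: freedom from "any Serious Adverse Event (SAE) through 30 days post procedure".

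**Planned analyses.** Section 10.6.1 plans a descriptive 30-day safety analysis of the 50 pivotal subjects, a descriptive 6-month analysis of the same subjects, and a final analysis of the primary hypothesis. Section 10.6.4 presents secondary endpoints descriptively.

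**The concern.** The study's stated objective includes safety. Subjects who lose the device after implantation are those in whom something has gone wrong, and their course after an explant, which Section 5.8 notes may be surgical, is relevant to the device's safety. The plan stops routine collection at that moment. Section 9.6 adds that events still open at discontinuation stay recorded as ongoing, so the outcome of the very event that led to removal may never be entered.

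Two consequences follow. The 30-day SAE record is incomplete for anyone explanted before day 30. And sites read two kinds of instruction, 36 months for all and discontinuation at removal, without a sentence that connects them.

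A lesser matter is reporting. In subjects who keep the device, late SAEs and deaths are collected, but the only safety proportion defined for 12 and 36 months cannot reflect them unless a device event also occurs.

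**Working it through.** The plan has no figure of its own on this point, so the check sets the sections side by side.

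**Step 1. When routine adverse event collection ends, by type of subject.**

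| Subject | Collection ends | Source |
|---|---|---|
| Keeps the device | 36-month visit, or earlier withdrawal or loss to follow-up | Sections 5.6, 5.7, 9.6 |
| Never implanted | Telephone contact at day 30 ± 14, i.e. day 30 − 14 = 16 to day 30 + 14 = 44 | Sections 5.2, 5.4.6 |
| Device removed on day d after the index procedure | Day d | Sections 5.4.9, 5.5 |

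If d is below 16, the explanted subject has less adverse event follow-up than any never-implanted subject contacted within the window. If d lies from 16 to 29, the explanted subject has less than one contacted at the nominal day 30. In both cases part of the 30-day SAE window goes unobserved.

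**Step 2. Does the Safety proportion change?** Suppose removal occurs on day d. At every Safety time point on or after d, the subject already counts, because removal is a device event. At time points before d, collection was still running. Events after d therefore cannot alter Safety at 6, 12 or 36 months. What is lost is the description of later harm, and a breakdown by component, if one were made, could show too few 30-day SAEs.

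**Step 3. Are the follow-up statements consistent?** Sections 3.1 and 10.5 carry no exception, and Section 5.4.3 none for removal. Against them stand Section 5.4.6 (30 days for never-implanted subjects), Section 5.4.8 (data recorded to 36 months or to withdrawal or discontinuation), Sections 5.4.9 and 5.5 (discontinuation at removal), Section 5.7 (anyone short of 36 months is a withdrawal) and Section 9.6 (reporting ends at completion or discontinuation). The second group can be read as exceptions to the first, but the first does not refer to them.

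**Step 4. What else could capture harm after removal?** UADE reporting (Section 9.2) names no cut-off at a subject's discontinuation, so it may capture some events, but only those in that restricted class. The Independent Data Reviewer (Section 9.8) sees accumulating study data and cannot review what was not collected. Return of the explanted device (Section 5.8) informs about the device, not about the subject's later course.

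**Step 5. Secondary point.** Take a subject who keeps the device and dies on day 200 with no earlier Safety event. The death is recorded (Section 9.6), coded (Section 9.7) and open to the Independent Data Reviewer (Section 9.8). Safety at 12 and 36 months is unchanged by it. No item in Section 10.6 names a table in which it would appear.

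**The case against.** **The sections do not really conflict.** Sections 5.4.6, 5.4.8, 5.4.9, 5.5, 5.7 and 9.6 form a workable general rule with exceptions, and the same-criteria sentence in Section 10.5 closes a description of three enrollment phases and may mean only that the phases are treated alike. This largely stands. A reader might infer a flat contradiction; the documents support something weaker, unqualified general statements beside specific exceptions that are not cross-referenced. Reconciling them is mainly a matter of wording. The loss of post-explant data remains under either reading.

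**Post-removal harm is not wholly lost.** Also right: UADE reporting may pick some of it up. It is accurate to say that such harm falls outside routine collection, not that it goes entirely unrecorded.

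**The Safety definition is deliberate.** Its split into day 0–30 SAEs and later device events mirrors the rows of the HELEX control table (Table 10.2.1). This stands, and it is why the definition should be left alone.

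**Late events are collected and overseen, and routine tables will probably show them.** This stands too. A reader might infer that late deaths and SAEs in subjects with the device in place are uncollected or unmonitored; Sections 9.6 to 9.8 say otherwise. Only the naming of a summary is missing, so that part is optional.

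**Conclusion.** The point holds as a cheap improvement of minor weight. The plan stops routine adverse event collection at device removal, which can leave an early explant with less follow-up than a subject never implanted and leaves the 30-day SAE window incomplete for that subject. The follow-up sections need to be reconciled.

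Its size cannot be put as a number of events: the documents give no number of removals and no late SAE rate, and the control table's counts are redacted. A reader might infer that the Safety proportion is biased; it is not, because removal already counts (Step 2). Nothing is concluded here about the primary test. Section 10.6.2 requires per-protocol subjects to complete evaluation through 6 months while Section 5.5 discontinues explanted subjects, and how those subjects enter the test is a separate question.

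The conclusion assumes that Sections 5.4.9 and 5.5 are applied as written, and that no other study document extends collection after removal. The late SAE and death summary is a secondary, optional suggestion.

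**What to change.** **Main change.** Amend Sections 5.4.9 and 5.5 so that adverse event and vital-status data are collected for a stated period after device removal, reaching at least day 30 after the index procedure so that the SAE window is complete. The existing telephone questionnaire could be adapted: the current day-30 contact would serve for removals before day 30, and a version timed from removal for later ones. The length of any further period is the sponsor's choice and should be written down. Then align Sections 3.1, 5.4.3 and 10.5, with explicit reference to the exceptions for never-implanted and explanted subjects.

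**Optional change.** Leave the Safety definition and the primary composite as they are. Beside them, present deaths and SAEs through 6, 12 and 36 months by a method that accounts for follow-up time, such as Kaplan-Meier or a rate per person-time, with numbers at risk. A crude proportion of all enrolled subjects would understate 36-month risk, because never-implanted subjects leave at about day 30 and explanted subjects at removal. Censoring at removal may itself be informative, which is a further reason for the main change. Show relatedness to device, procedure and study medication separately, each on the Section 9.3 scale.

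**Cost.** One extra contact per explanted subject, a re-timed form and edits to a few sections; the optional part is one descriptive summary from data already collected. No test, decision rule or sample size needs to be altered to make these changes. The safety data may look slightly less favourable.
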